- 27. Have pre-existing demyelinating disorder such as multiple sclerosis, or other severe neurological deficits.
- 28. Have current alcohol and/or drug abuse, or a history of, in the past 2 years which, in the opinion of the investigator, could create a risk for the participant's health or protocol adherence.
- 29. Have had major surgery within 4 weeks of screening, or scheduled to occur during the study, excluding diagnostic surgery.
- 30. Previous treatment with total lymphoid irradiation.
- 31. Grade 3 or greater laboratory abnormality based on the Common Terminology Criteria for Adverse Events (CTCAE) v 4.03 (Appendix 14) except the following that are allowed: Participants with abnormal aspartate aminotransferase (AST), alanine aminotransferase (ALT), lactate dehydrogenase (LDH), aldolase, and CK lab values if these values are determined by the investigator to be related to muscle involvement, and if γ glutamyl transferase (GGT) <1.5 upper limit normal.
- 32. Known exposure to anti-beta Interferon, (PF-06823859) or any type of anti-beta interferon therapy.

4.3. Inclusion Criteria, Amended Stage 2

If a participant meets eligibility for both the Stage 2, (skin focused cohort) and the Stage 3, (muscle disease cohort) the patient should be placed in the Stage 3 muscle disease cohort.

All inclusion criteria is the same as Stage 1 and Stage 2 with the exception to Inclusion Criteria #6.

6. Willing to provide at least (8) vs. 6 skin punch biopsies; (4) skin punch biopsies at pre-dose Day 1 Visit 2, (2) skin punch biopsies at Week 12, Visit 6 and (2) skin punch biopsies at Week 24 Visit 9.

4.4. Exclusion Criteria, Amended Stage 2

All exclusion criteria is the same as Stage 1 and Stage 2 with the exception of Exclusion Criterion #7 Abnormal labs and Exclusion Criterion #12 related to stable dosing of concomitant medications:

Exclusion Criterion #7:

- Hemoglobin <9 g/dL;
- Creatinine clearance <50 mL/min according to modified Cockcroft-Gault equation.

Exclusion Criterion #12:

- Any change in dose of an immunosuppressive/immunomodulatory or antimalarial agent. Dose must be stable for 60 days prior to Day 1 and remain stable through Week 24.
- Inhaled immunosuppressive agents can be used during the study however must be on a stable dose 60 days prior to Day 1 and remain stable through Week 24. (Immunosuppressive ophthalmic drops are allowed without any restrictions).
- Disease -modifying antirheumatic drugs (DMARD)s, (methotrexate, sulfasalazine, hydroxychloroquine, and leflunomide). Less frequently used medications include gold salts, azathioprine, and cyclosporine. Dose must be stable for 60 days prior to Day 1 and remain stable through Week 24.

4.5. Inclusion Criteria, Stage 3

- 1. Evidence of a personally signed and dated informed consent document indicating that the participant has been informed of all pertinent aspects of the study.
- 2. Male and or female participants between the ages of ≥ 18 and ≤ 80 years old at the time of signing the informed consent.
- 3. Meets one of the following two criteria:
- MMT-8 ≤136/150 and PhGA, VAS ≥3 cm (0-10 cm) by visual analog scale (VAS) (Appendix 21).
- Sum of PhGA, VAS, PtGA, and extramuscular global assessment VAS scores (Appendix 20) is ≥10 cm (0-10 cm) VAS for each).
- 4. Participant has failed at least two or more adequate courses of an immunosuppressive agent or immunomodulatory agent, including IVIG, at a dose known to be effective for rheumatologic diseases.
- 5. Participant has had a standard work up for dermatomyositis (prior to) baseline.
 - a. Stable interstitial lung disease related to DM that is not severe in the opinion of the investigator is allowed, ie, no supplemental oxygen permitted.
 - b. If their DM diagnosis is within 2 years of the screening visit, then they must have completed either:
 - Age appropriate malignancy screening eg, computerized tomography, (CT) of the chest/abdomen/pelvis if indicated;

or

- PET CT of chest/abdomen/pelvis at least once by the baseline visit.
- 6. Male participants able to father children and female participants of childbearing potential must agree to adhere to the methods of contraception. See Appendix 25 throughout the duration of the study, including the follow-up period until the end of study.
 - Participants in Germany: please see guidelines for Contraception Methods in Appendix 24.
- 7. Female participants of non-childbearing potential must meet at least 1 of the following criteria:
 - a. Achieved postmenopausal status, defined as follows: cessation of regular menses for at least 12 consecutive months with no alternative pathological or physiological cause; status may be confirmed with a serum follicle-stimulating hormone (FSH) level confirming the postmenopausal state.
 - b. Have undergone a documented hysterectomy and/or bilateral oophorectomy.
 - c. Have medically confirmed ovarian failure.
 - d. All other female participants (including female participants with tubal ligations) are considered to be of childbearing potential.

8. Willing and able to comply with scheduled visits, treatment plan, laboratory tests and other study procedures.

4.6. Exclusion Criteria, Stage 3

- 1. Investigator site staff members directly involved in the conduct of the study and their family members, site staff members otherwise supervised by the investigator, or participants who are Pfizer employees, including their family members, directly involved in the conduct of the study.
- 2. Other acute or chronic medical or psychiatric condition including recent (within the past year) or active suicidal ideation or behavior or laboratory abnormality that may increase the risk associated with study participation or investigational product administration or may interfere with the interpretation of study results and, in the judgment of the investigator, would make the participant inappropriate for entry into this study.
- 3. Any psychiatric condition including recent or active suicidal ideation or behavior that meets any of the following criteria:
 - Clinically significant depression by Patient Health Questionnaire 8- item depression measure (PHQ-8) total score ≥15 (Appendix 4) (completed during the screening visit).
 - Suicidal ideation associated with actual intent and a method or plan in the past year: "Yes" answers on items 4 or 5 of Columbia-Suicide Severity Rating Scale during the conduct of the study (C-SSRS; Appendix 5) (completed prior to Day 1 Dosing).
 - Previous history of suicidal behaviors in the past 5 years: "Yes" answer (for events that occurred in the past 5 years) to any of the suicidal behavior items of the C-SSRS; Appendix 6).
 - Any lifetime history of serious or recurrent suicidal behavior.
 - The presence of any current major psychiatric disorder that is not explicitly permitted in the inclusion/exclusion criteria.
 - In the opinion of the investigator, exclusion is required.
- 4. Intake of >20 mg oral prednisone/day, or equivalent.
- 5. Drug induced myopathy, metabolic myopathy, muscular dystrophy, cancer associated DM, mixed connective tissue disease-associated DM, (eg, overlap syndrome) and polymyositis.

- 6. Significant concurrent disease or conditions other than DM that may influence response to the study drug or safety.
- 7. Abnormal labs:
 - Hemoglobin <9 g/dL;
 - Neutrophils $<1.0 \times 10^9/L$;
 - Lymphocytes <500 cells/uL;
 - Platelets $<75 \times 10^{9}/L;$
 - Creatinine clearance <50 ml/min according to modified Cockcroft-Gault equation;
 - Alkaline phosphatase >2.5 x upper normal limit;
 - Total bilirubin ≥ 1.5 x upper limit of normal.
 - *Note*: Elevation of aspartate aminotransferase (AST), alanine aminotransferase (ALT), lactate dehydrogenase (LDH), creatinine kinase (CK) or aldolase due to muscle involvement (in the opinion of the investigator) are allowed if gamma glutamyl transferase, GGT <1.5 upper limit normal.
 - *Note:* Screening laboratory tests with abnormal results may be repeated once to confirm abnormal results within the 5-week screening period. If results return to normal within the 5-week screening period, the participant may enter the study.
- 8. Participation in other studies involving investigational drug(s) within 30 days prior to study entry. For biologics, 5 half-lives or 180 days preceding the first dose of the investigational product (whichever is longer). This applies prior to study entry and/or during study participation.
- 9. Pregnant female participants; breastfeeding female participants; fertile male participants and female participants of childbearing potential who are unwilling or unable to adhere to the methods of contraception. See Appendix 25 as outlined in this protocol for the duration of the study and for 5 months after the after the last dose of investigational product.
- 10. Have received the following within 180 days of Day 1: (See Appendix 15 and Appendix 16).
 - A biologic investigational agent. An investigational agent is defined as any drug not approved for sale in the country in which it is being used.

- IV or oral cyclophosphamide, belimumab or any anti-B-Lymphocyte Stimulator (anti-BLyS or anti-B-cell activating factor [anti-BAFF] agent).
- Required 3 or more courses of systemic corticosteroids for concomitant conditions (eg, asthma, Crohn's disease, ulcerative colitis, systemic vasculitis, atopic dermatitis).
- 11. Have received the following within 90 days of Day 1: (See Appendix 15 and Appendix 16).
 - Anti-TNF therapy (eg, infliximab, etanercept, adalimumab).
 - High dose oral corticosteroids (>100 mg/day prednisone or equivalent) or pulse IV doses.
 - Plasmapheresis.
- 12. Have received the following within 60 days of Day 1: (See Appendix 15 and Appendix 16).
 - Any intra muscular (IM) or IV steroid injection. (same as above).
 - Tofacitinib or any other Janus kinase (JAK) inhibitors.
 - Any change in dose of an immunosuppressive/immunomodulatory or antimalarial agent. Dose must be stable for 60 days prior to Day 1 and remain stable through Week 24.
 - Inhaled immunosuppressive agents can be used during the study for ILD related to DM; however, must be on a stable dose 60 days prior to Day 1 and remain stable through Week 24. (Immunosuppressive ophthalmic drops are allowed without any restrictions).
 - Disease -modifying antirheumatic drugs (DMARD)s, (methotrexate, sulfasalazine, hydroxychloroquine, and leflunomide). Less frequently used medications include gold salts, azathioprine, and cyclosporine. Dose must be stable for 60 days prior to Day 1 and remain stable through Week 24.
 - Participants may be on one of the following cytotoxic agents: methotrexate, azathioprine, leflunomide, mycophenolate, or 6 MP, but not on any combination of these cytotoxic agents.

Use of IV or IM antibacterials, antivirals, antifungals, or anti-parasitic agents within 60 days of Day 1. Substitution of IM agents for oral agents because of gastro intestinal, (GI) intolerance may be acceptable, as long as it does not otherwise meet the criteria for a serious infection (requires hospitalization or use of other IV antibiotics) (See exclusion #24).

- 13. Have received within 6 weeks of Day 1: (See Appendix 15 and Appendix 16).
 - A live (live attenuated) vaccine.
- 14. Have received any of the following within 30 days of Day 1: (See Appendix 15 and Appendix 16).
 - Any intra-articular steroid injection.
 - Any new, or change in dose of a corticosteroid or equivalent.
 - Any new, or change in dose of intravenous immunoglobulin (IVIG); (Must be on a stable dose for 30 days).
 - Oral tacrolimus.
- 15. Have received any of the following within 14 days prior to Day 1: (See Appendix 15 and Appendix 16).
 - Use of oral antibiotics to treat an active infection within 14 days of Day 1.
 - Topical calcineurin inhibitors.
- 16. Have been treated with any B-cell depleting agents such as rituximab (or other CD20+ directed therapies, or epratuzumab, or anti-CD52 [alemtuzumab]), or Transmembrane Activator and CAML Interactor (TACI)-Ig, within 12 months prior to Day 1. In addition, participants that have been treated with rituximab, or TACI-Ig, serum total immunoglobulin should be checked prior to study entry.
- 17. Have a history of a major organ transplant (eg, heart, lung, kidney, liver) or hematopoietic stem cell/marrow transplant.
- 18. Active bacterial, viral, fungal, mycobacterial or other infections (including but not limited to tuberculosis [TB] and atypical mycobacterial disease, granulomatous disease on chest x-ray). History of recurrent bacterial, viral, fungal, mycobacterial or other infections (including but not limited to TB and atypical mycobacterial disease, granulomatous disease on chest x-ray) that would substantially increase the risk to the participant if he or she participates in the study.
- 19. Have clinically significant finding on a chest radiograph (or other appropriate diagnostic imaging study previously completed within 12 weeks prior to Day 1 such as computed tomography [CT] or magnetic resonance imaging [MRI]) such as the presence of TB, general infection, heart failure or malignancy. Chest imaging must be performed during the 5-week screening period or if diagnostic imaging was previously completed within 12 weeks prior to Day 1.

20. Infected with Mycobacterium tuberculosis (TB) as defined by any of the following:

A positive Interferon Gamma Release Assay (IGRA) test performed at or within the 12 weeks prior to Day 1 is exclusionary; a negative test is required for eligibility. The following are acceptable IGRA assays: QuantiFERON[®] TB Gold In-Tube test (QFT-GIT) and QuantiFERON[®] - TB Gold test (QFT-G), and T-spot[®] TB test. If T-spot[®] TB test was completed within 12 weeks prior to Day 1, this is acceptable, however this test type cannot be offered for participants requiring the test during screening, or at any time during the study.

- In participants with a history of Bacillus Calmette-Guérin (BCG) vaccination, the IGRA test is strongly recommended since the Mantoux test (tuberculin, purified protein derivative [PPD] skin test) may be positive due to vaccination.
- If the results of the IGRA are indeterminate, the test may be repeated, and if a negative result is obtained, enrollment may proceed. A positive test on repeat is exclusionary.
- Participants with repeat indeterminate IGRA results may be enrolled after consultation with an infectious disease and/or pulmonary specialist who determines that the risk of infection is low (ie, participant would be acceptable for immunosuppressant treatment without additional action).
- Participants who test positive for IGRA, but in the opinion of the principal investigator (PI) are at low risk of TB infection, may be referred to an infectious disease and/or pulmonary specialist for consultation and potential IGRA test repeated once. Participants will be eligible if the repeat test is negative before the randomization and an infectious disease and/or pulmonary specialist determines that the risk of infection is low (ie, participant would be acceptable for immunosuppressant treatment without additional action).
- Chest radiograph taken at screening with changes suggestive of active TB infection, unless previously performed and documented within 12 weeks prior to Day 1.
- A participant who has been treated or is currently being treated for active or latent TB infection is to be excluded.
- A participant with a history of either untreated or inadequately treated latent or active TB infection is to be excluded.
- 21. Have a history of any lymphoproliferative disorder such as Epstein Barr Virus (EBV) related lymphoproliferative disorder, history of lymphoma, leukemia, or signs and symptoms suggestive of current lymphatic or lymphoid disease.

- 22. Have a history (single episode) of disseminated herpes zoster or disseminated herpes simplex, or recurrent (more than 1 episode of) localized, dermatomal herpes zoster.
- 23. Known history of the following viruses:
 - Human immunodeficiency (HIV) based on documented history with positive serological test, or positive HIV serological test at screening.

Note: a documented negative HIV test within 3 months of screening is acceptable and does not need to be repeated.

- Have positive test for hepatitis B surface antigen (HBsAg), total hepatitis B core antibody (anti-HBcAb; also called anti-HBc), hepatitis B surface antibody (HBsAb), and/or HCV Ab.
- All participants will be screened for HBsAg and HBcAb; participants who are HBsAg positive will be screen-failed. Participants who are HBsAg negative but HBcAb positive will be reflex-tested for HBsAb and, if HBsAb positive, may enroll; if hepatitis B surface antibody test, (HBsAb) negative, they will be screen-failed. Participants who are positive for HCV Ab will be screen-failed.

24. Have required management of acute or chronic infections as follows:

- Currently on any suppressive therapy for a chronic infection (such as pneumocystis, cytomegalovirus [CMV], and atypical mycobacteria) that, in the opinion of the investigator and sponsor, would place the participant at risk for reactivation. Participants receiving prophylactic therapy for prior outbreaks of herpes simplex virus or herpes zoster may be enrolled with the expectation that this treatment will continue for the duration of the study.
- Hospitalization for treatment of serious infections within 60 days of Day 1, see exclusion (#12).
- 25. Have acute coronary syndrome (eg, myocardial infarction, unstable angina pectoris) or any history of significant cerebrovascular disease within 24 weeks of screening. A screening 12-lead electrocardiogram (ECG) that demonstrates clinically significant abnormalities requiring treatment (eg, acute myocardial infarction, serious tachy- or brady- arrhythmias) or that is indicative of serious underlying heart disease (eg, cardiomyopathy, major congenital heart disease, low voltage in all leads, Wolff-Parkinson-White syndrome).
- 26. Have cancer or a history of cancer within 5 years of screening (other than adequately treated cutaneous basal cell, squamous cell carcinoma, or carcinoma in situ of the uterine cervix with no evidence of recurrence within the previous 5 years).
- 27. Have pre-existing demyelinating disorder such as multiple sclerosis, or other severe neurological deficits.

- 28. Have current alcohol and/or drug abuse, or a history of, in the past 2 years which, in the opinion of the investigator, could create a risk for the participant's health or protocol adherence.
- 29. Have had major surgery within 4 weeks of screening, or scheduled to occur during the study, excluding diagnostic surgery.
- 30. Previous treatment with total lymphoid irradiation.
- 31. Grade 3 or greater laboratory abnormality based on the Common Terminology Criteria for Adverse Events (CTCAE) v 4.03 (See Appendix 14) except the following that are allowed: Participants with abnormal aspartate aminotransferase (AST), alanine aminotransferase (ALT), lactate dehydrogenase (LDH), aldolase, and CK lab values if these values are determined by the investigator to be related to muscle involvement, and if γ glutamyl transferase (GGT) <1.5 upper limit normal.

- 32. Known exposure to anti-beta Interferon, (PF-06823859) or any type of anti-beta interferon therapy.
- 33. Participant has severe muscle damage defined as a global muscle damage score >5 on a 10 cm VAS scale which is a component on the Myositis Damage Index (MDI) Appendix 23.

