 - Participants in Germany: please see guidelines for Contraception Methods in Appendix 24.

10. Have received the following within 180 days of Day 1:

- A biologic investigational agent. An investigational agent is defined as any drug not approved for sale in the country in which it is being used.
- IV or oral cyclophosphamide, belimumab or any anti-B-Lymphocyte Stimulator (anti-BLyS or anti-B-cell activating factor [anti-BAFF] agent).
- Required 3 or more courses of systemic corticosteroids for concomitant conditions (eg, asthma, Crohn's disease, ulcerative colitis, systemic vasculitis, atopic dermatitis).

11. Have received the following within 90 days of Day 1:

- Anti-TNF therapy (eg, infliximab, etanercept, adalimumab).
- High dose oral corticosteroids (>100 mg/day prednisone or equivalent) or pulse IV doses.
- Plasmapheresis.
- 12. Have received the following within 60 days of Day 1:
 - Any intra muscular (IM) or IV steroid injection.
 - Tofacitinib or any other Janus kinase (JAK) inhibitors.

- Any change in dose of an immunosuppressive/immunomodulatory or antimalarial agent. Dose must be stable for 60 days prior to Day 1 and remain stable through Week 12.
- Inhaled immunosuppressive agents can be used during the study however must be on a stable dose 60 days prior to Day 1 and remain stable through Week 12. (Immunosuppressive ophthalmic drops are allowed without any restrictions).
- Disease -modifying antirheumatic drugs (DMARD)s, (methotrexate, sulfasalazine, hydroxychloroquine, and leflunomide). Less frequently used medications include gold salts, azathioprine, and cyclosporine. Dose must be stable for 60 days prior to Day 1 and remain stable through Week 12.
- Participants may be on one of the following cytotoxic agents: methotrexate, azathioprine, leflunomide, mycophenolate, or 6 MP, but not on any combination of these cytotoxic agents.

Use of IV or IM antibacterials, antivirals, antifungals, or anti-parasitic agents within 60 days of Day 1. Substitution of IM agents for oral agents because of gastro intestinal, (GI) intolerance may be acceptable, as long as it does not otherwise meet the criteria for a serious infection (requires hospitalization or use of other IV antibiotics) (See exclusion #24).

13. Have received within 6 weeks of Day 1:

- A live (live attenuated) vaccine.
- 14. Have received any of the following within 30 days of Day 1:
 - Any intra-articular steroid injection.

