Appendix 14. Guidelines for Participant Safety Monitoring and Discontinuation

These guidelines for participant safety monitoring and discontinuation are to be applied to all participants in study C0251002. Additional individual participant monitoring is at the discretion of the investigator and dependent on any perceived safety concerns. Unscheduled clinical labs may be obtained at any time during the study to assess such concerns, and a participant may be withdrawn at any time at the discretion of the investigator.

Monitoring

Please Note: For Participants with DM who experience elevated AST, ALT, LDH, Aldolase, and CK, due to muscle involvement the investigator should determine whether or not these are related to the existing condition of DM or if these lab abnormalities are related to another condition. (If related to DM, GGT should be <1.5 ULN) Information should be provided in the source documentation with rationale related to any lab abnormalities.

The following laboratory abnormalities require re-testing within 1 week:

- Any single AST and/or ALT elevation ≥3 times the upper limit of normal (repeat laboratory testing should include albumin, creatine kinase, total bilirubin, direct and indirect bilirubin, GGT, PT [prothrombin time] with INR [international normalized ratio], and alkaline phosphatase), regardless of the total bilirubin. (Please note that 3 times the upper limit of normal increases in ALT, AST need confirmation on separate blood draw before undertaking thorough evaluation for liver injury);
- For women of child-bearing potential with any positive urine β-hCG test, the participant will have study drug interrupted and a serum sample submitted to the central laboratory for β-hCG testing.

Discontinuation

Investigators are encouraged to discuss with the sponsor's Clinical team as soon as possible, and participants are to be discontinued from treatment if any of the following occur during the study:

- Serious infections defined as any infection (viral, bacterial, and fungal) requiring parenteral antimicrobial therapy, hospitalization for treatment, or meeting other criteria that require the infection to be classified as serious adverse event;
- Other serious or severe AEs, at the discretion of the investigator or sponsor;

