- If there are "yes" answers on items 4, 5, or on any behavior question of the C-SSRS, the participant will be discontinued from treatment and referred to a mental health professional for appropriate evaluation and treatment (if the participant cannot be seen by a mental health professional within 24 hours, then the participant should be sent to a local emergency room for psychiatric assessment);

- All of the following laboratory abnormalities require discontinuation if they are confirmed (confirmation through re-testing is expected to occur within 1 week):
 - Two sequential AST or ALT elevation ≥ 3 times the upper limit of normal with at least one total bilirubin value ≥ 2 times the upper limit of normal;^a
 - Two sequential AST or ALT elevation ≥3 times the upper limit of normal accompanied by signs or symptoms consistent with hepatic injury;^a
 - Two sequential AST or ALT elevation ≥5 times the upper limit of normal, regardless of total bilirubin or accompanying signs or symptoms;^a
 - Female participants found to be pregnant during the study;
 - Other serious or severe AEs, after consultation with the Pfizer medical monitor or designee.
- a. In each case, there is a need for additional investigations, such as review of ethanol, recreational drug and dietary supplement consumption; testing for acute hepatitis A, B or C infection and biliary tract imaging should be promptly discussed with the Pfizer medical monitor or designee.

Use of prohibited medications require participant discontinuation as reflected in Appendix 16:

Please refer to Appendix 16 for all inclusive prohibited medication listing.

Any participant meeting discontinuation criteria must enter follow-up with their first follow-up visit occurring 1 week after their last dose whenever possible, until the event has returned to normal or baseline levels or is deemed clinically stable. The procedures scheduled for the early withdrawal visit will be performed on the last day the participant takes the IP or as soon as possible thereafter. The only exception to this is when a participant specifically withdraws consent for any further contact with him/her or persons previously authorized by the participant to provide this information.

Participants will be followed post drug discontinuation for 5 months. Additional follow-up visits may occur as needed until any clinically relevant abnormalities or adverse events have resolved, returned to a baseline state, or are deemed clinically stable.

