Appendix 15. Time needed for Washout of Prohibited Medication or Medication Stabilization Prior to Day 1

180 days (6 months) prior to DAY 1

- B-cell depleting agents, (rituximab, epratuzumab, alemtuzumab, or TACI-Ig). In addition, participants that have been treated with rituximab, or TACI-g, (serum total immunoglobulin should be checked prior to study entry);
- Investigational biologic agent;
- IV or Oral Cyclophosphamide;
- Belimumab; or
- Any B-Lymphocyte Stimulator, (BLys or anti BAFF agent).

90 Days (3 months) prior to DAY 1

- Anti-TNF therapy, (infliximab, etanercept, adalimumab).
- High dose oral corticosteroids (>100 mg/day prednisone, or equivalent) or pulse IV doses.
- Plasmapheresis.

60 Days (2 months) prior to DAY 1

- Any IV or IM steroid injection
- Tofacitinib or any other JAK inhibitor
- Stable dose of antimalarial agent 60 days,
- Stable dose of immunosuppressive/immunomodulatory agent (60 days)
- INHALED immunosuppressive agents (STABLE 60 days prior to Day 1, dose must remain stable during the study)
- DMARDs, (methotrexate, sulfasalazine, hydroxychloroquine, and leflunomide. Less frequently used medications include gold salts, azathioprine, and cyclosporine) Dose must be stable for 60 days and remain stable during the treatment.
- Participants may be on one of the following cytotoxic agents: Methotrexate,(MTX), Azathioprine, (AZA), leflunominde, mycophenolate, or 6- Mercaptopurine (MP), but not on any combination of these cytotoxic agents.
 - Replacement of one immunosuppressive medication or antimalarial drug for another may be permitted for safety related issues after discussion with the sponsor.

42 Days (6 weeks prior to Day 1)

• Live or attenuated vaccine.

30 Days (1 month prior to Day 1)

- Intra articular steroid injection.
- Must be on a stable dose of corticosteroid or equivalent for 30 days.
- Must be on a stable dose of IVIG for 30 days.
- Oral Tacrolimus requires a 30 day washout prior to Day 1 and is prohibited throughout the treatment period.

14 Days (2 weeks prior to Day 1)

- Topical calcineurin inhibitors, (eg, topical tacrolimus, pimecrolimus) require a 14 day washout prior to Day 1 and are prohibited throughout the treatment period.
- A stable dose of topical immunosuppressant of any strength used on the scalp is permitted throughout the study, with the exception of prohibited medications.

Marketed Biologics (prior to Day 1)

• Marketed Biologics require a five half-life washout period.

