Appendix 1	l 6. List	t of Prohibited	and Permitted	Concomitant	Medications
------------	-----------	-----------------	---------------	-------------	-------------

Medications		C0251002	Follow-up Period
		Treatment Period Day 1-Week 12 (Stage 2)	-
		Treatment Period Day 1-Week 24 (Amended Stage 2 (Amended Stage 3)	
	I		
Corticosteroids	Parenteral injections (intra-articular) IA, IM, or IV)	Prohibited	Permitted
	Oral (prednisone or equivalent)	Permitted (Stage 2)	Permitted
		 Prednisone ≤15 mg/day or equivalent provided dose is stable for at least 30 days prior to Day 1. 	
		Permitted (Stage 3)	
		 Prednisone ≤20 mg/day or equivalent provided dose is stable for at least 30 days prior to Day 1. 	
		• Tapering of steroids is permitted after Week 24, in Amended Stage 2 and Stage 3.	
Immunosuppressive or immunomodulatory agents including methotrexate (MTX), azathioprine (AZA), leflunomide, mycophenolate (including mycophenolate mofetil, mycophenolate mofetil hydrochloride, and mycophenolate sodium), or 6-mercaptopurine (6-MP).		Permitted	Permitted
		• Provided pre-existing dose is stable for at least 60 days prior to Day 1.	
		• No new immunosuppressives or increase in dose is allowed during the treatment period.	
		• Participants can be on 1 of the following cytotoxic agents: MTX, AZA, leflunomide, mycophenolate, or 6-MP, but not on any combination of these cytotoxic agents.	
Antimalarials (eg, hydroxychloroquine, chloroquine, quinacrine)		Permitted	Permitted
		• Provided pre-existing dose is stable for at least 60 days prior to Day 1.	
		• No new antimalarial drugs or increase in dose is allowed during the treatment period.	
Thalidomide, tacrolimus, or mizoribine		Prohibited	Permitted
		• Any form of tacrolimus or any form of a topical calcineurin inhibitor, (TCI) is not allowed.	
Immunosuppressive topical		Permitted	Permitted
		• Immunosuppressive ointment for the scalp. Stable dose for 14 days prior to Day 1.	
Topical calcineurin inhibitors		Prohibited	Permitted
Immunosuppressive eye drops		Permitted	Permitted

Medications	C0251002	Follow-up Period
	Treatment Period Day 1-Week 12 (Stage 2)	_
	Treatment Period Day 1-Week 24 (Amended Stage 2	
	(Amended Stage 3)	
Investigational or marketed biologics (eg, abatacept, tocilizumab, TNF inhibitors)	Prohibited	Prohibited
Cyclophosphamide or chlorambucil	Prohibited	Permitted
Cyclosporine	Prohibited	Permitted
Other investigational drugs or investigational combinations	Prohibited	Prohibited

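### Cyclosporine at a stable dose is accepted by exclusion #12 and Appendix 15 but prohibited by Appendix 16, so in Stage 2, Amended Stage 2 and Stage 3 an eligible participant can meet a treatment-discontinuation rule from Day 1

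*Protocol*

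**What the plan says.** Four parts of the protocol bear on cyclosporine.

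- **Exclusion #12** (Sections 4.2, 4.4 and 4.6) names it in the bullet on disease-modifying drugs: "Less frequently used medications include gold salts, azathioprine, and cyclosporine". For Stages 1 and 2 the attached condition is "Dose must be stable for 60 days prior to Day 1 and remain stable through Week 12". For Amended Stage 2 and Stage 3 it is "Dose must be stable for 60 days prior to Day 1 and remain stable through Week 24".
- **Appendix 15**, under the 60-day heading, repeats this: "Less frequently used medications include gold salts, azathioprine, and cyclosporine) Dose must be stable for 60 days and remain stable during the treatment".
- **Appendix 16** gives the drug its own row, "Cyclosporine Prohibited Permitted". The first entry is for the treatment period and the second for follow-up. The row has no stable-dose exception.
- **Appendix 14** introduces its list with "participants are to be discontinued from treatment if any of the following occur during the study" and adds "Use of prohibited medications require participant discontinuation as reflected in Appendix 16".

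In the SAP, Sections 6.1.1.2, 6.2.1.3 and 6.3.2.1.1 each describe an analysis that may be run treating prohibited-medication use as an intercurrent event. Visits after the discontinuation criterion is met are censored.

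**The concern.** An entry rule and a stopping rule disagree about the same drug. A dose that has to stay stable through Week 12 or Week 24 is a dose that is still being taken, so exclusion #12 and Appendix 15 presume continued use over the very period in which Appendix 16 forbids it. One site could keep such a participant on treatment and another could discontinue the same kind of participant, each with protocol text in support. A person could be randomized and dosed, then taken off treatment for a drug that the entry criteria had accepted.

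For the analysis, the flag that drives the prohibited-medication sensitivity analyses would depend on which appendix the programmer followed. It would be equally unclear whether the use counts as a major deviation for the per-protocol sets in SAP Section 4.2.

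**Working it through.** The plan gives no figure to reproduce. The check is to set the passages side by side and follow a current cyclosporine user through them.

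1. **Continues at a stable dose.** Exclusion #12 is satisfied and so is Appendix 15. The Appendix 16 column for the treatment period, headed "Treatment Period Day 1-Week 12 (Stage 2" for that stage, starts on Day 1, so the drug is prohibited from the first dose. Appendix 14 then calls for discontinuation of treatment.
2. **Stops within the 60 days before Day 1.** Appendix 16 is satisfied, but the dose has changed inside the 60-day window, so the stability condition in exclusion #12 and Appendix 15 is not met.
3. **Result.** No route satisfies all the passages for a current user.

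The handling of another drug shows what a consistent prohibition looks like in this protocol. Oral tacrolimus has a 30-day exclusion (#14), a 30-day washout in Appendix 15 that also states the prohibition, and a prohibited entry in Appendix 16. Cyclosporine has no washout anywhere.

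**Scope.** The Appendix 16 headings name Stage 2, Amended Stage 2 and what they call Amended Stage 3, taken here to mean Stage 3. They do not name Stage 1. Immunosuppressive eye drops are separately permitted, so the conflict concerns other forms of the drug.

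**Consequence for the data.** Appendix 14 and Section 6.2.8 keep a participant who stops treatment in follow-up. The primary analysis (SAP 6.2.1.1) and the main TIS analysis (SAP 6.3.2.1) use observed data and have no censoring rule for prohibited medication. In the optional analyses, a criterion met on Day 1 would put every post-baseline visit after it.

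**Size, for one hypothetical participant** (planning numbers from Protocol 9.1.2 and 9.1.3):

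- Pooled placebo, 11 completers: 1/11 = 9.1%.
- 150 mg, 10 completers: 1/10 = 10%.
- Stage 3 arm, 8 to 4 completers: 1/8 = 12.5% to 1/4 = 25%.

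Stage 1 was planned to supply 8 placebo completers (Protocol 9.1.1). About 11 − 8 = 3 of the pooled placebo completers would therefore come from the stages where the conflict applies.

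**The case against.** The strongest defence is that the documents offer a way out. Section 5.8.1 allows stable background treatment only if it is a permitted treatment, Appendix 14 describes Appendix 16 as the complete list of prohibited drugs, and a note to Appendix 16 tells sites to contact the study team with questions. A careful site would ask before randomizing. That stands, and it makes the Day 1 conflict a possible outcome rather than a certain one. It does not settle the matter, because Section 5.8.1 sends the reader to Appendices 15 and 16, which disagree, and Sections 5.8.2 and 5.8.3 do the same.

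A second defence is that #12 is an exclusion criterion whose opening words concern drugs received within 60 days of Day 1, so it grants no express permission. Read literally, however, it would also bar methotrexate, azathioprine, leflunomide and hydroxychloroquine. Appendix 16 permits these at a stable dose, and the requirement to remain stable through Week 12 or 24 would have no meaning.

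Three stronger readings are tempting, and the documents do not support them.

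- A reader might infer that the participant is withdrawn from the study. The text requires stopping treatment and entering follow-up.
- A reader might infer that the primary estimate loses data. No censoring rule applies there, and the sensitivity analyses that do censor are optional.
- A reader might extend the stopping rule to Stage 1. The Appendix 16 headings do not name it. The document history also records the Appendix 14 reference to Appendix 16 as an Amendment 5 clarification of May 2021, after all 32 Stage 1 participants had reached Week 12 for the interim analysis of April 2020.

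**Conclusion.** The contradiction is real and should be corrected. In Stage 2, Amended Stage 2 and Stage 3, a participant on stable non-ophthalmic cyclosporine can meet the entry criteria and a mandatory treatment-discontinuation rule at the same time, and no reading of the text resolves this.

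Its reach is limited. It affects how sites act, the optional prohibited-medication sensitivity analyses and possibly the per-protocol sets. It does not by itself remove anyone from the primary analysis.

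The number affected is unknown and may be zero, since the protocol itself calls the drug less frequently used. The percentages above assume one affected participant and the planned completer counts. They are not a forecast, and as shares of censored data they apply only to the optional analyses. The conclusion also assumes that exclusion #12 means what its stability condition implies, namely that the listed drugs may continue.

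**What to change.** Reconcile exclusion #12 in all its versions (Sections 4.2, 4.4, 4.6) with Appendices 14, 15 and 16, so that cyclosporine has a single status in the treatment period, and say explicitly which stages Appendix 16 covers. Then state in the SAP, before unblinding, how cyclosporine use is flagged for the prohibited-medication analyses and for the major-deviation list, in line with that status. Which status applies is a clinical decision for the sponsor's clinicians.

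The cost is a protocol clarification letter or amendment wording and a matching line in the SAP. No design element or sample size changes.
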